4.2 Exclusion Criteria

201. Patients with acute promyelocytic leukemia (APML)
202. Active extramedullary AML in the central nervous system (CNS)
203. Known hypersensitivity to immunoglobulins
204. White blood cells (WBC) > 15,000 cells/mcL (15 cells x 10⁹/L) at screening (hydroxyurea is permitted to enable eligibility)
205. Subjects with a prior or concurrent malignancy whose natural history or treatment is anticipated to interfere with the safety or efficacy assessment of the investigational regimen.

Exception: Subjects with prior or concurrent malignancy not anticipated to interfere with the safety or efficacy assessment of the investigational regimen may be included only after discussion with the Amgen Medical Monitor.

206. For R/R AML subjects only, autologous HSCT within 6 weeks prior to start of AMG 427 treatment (MRD+ subjects may be enrolled only after discussion with sponsor)

207. For R/R AML subjects only, allogeneic HSCT within 3 months prior to start of AMG 427 treatment (MRD+ subjects may be enrolled only after discussion with sponsor)
208. Any graft-versus-host disease requiring systemic therapy with immunomodulators
209. History or evidence of significant cardiovascular risk including any of the following: symptomatic congestive heart failure, unstable angina, clinically significant arrhythmias (eg, ventricular fibrillation, ventricular tachycardia etc.), recent coronary angioplasty, intra-cardiac defibrillators or any clinically relevant concurrent disorder that may pose a risk to subject safety or interfere with study evaluation, procedures, or completion
210. History of arterial thrombosis (eg, stroke or transient ischemic attack) in the past 3 months
211. Active infection requiring intravenous antibiotics within 1 week of study enrollment (day 1). Antibiotics may be administered for prophylaxis as per institutional standards up to and after enrollment.
212. Known positive test for human immunodeficiency virus (HIV)
213. Positive for hepatitis B surface antigen (HepBsAg)
214. Positive for hepatitis C or chronic hepatitis C

Possible exceptions: acute hepatitis C and completely cleared of the virus (demonstrated by negative viral load), chronic hepatitis C with undetectable viral load defined by sustained virologic response 24 weeks (SVR24) after completion of anti-hepatitis C treatment.
215. Live vaccination(s) within 4 weeks before the start of AMG 427 treatment on day 1, during treatment, and until the end of the last study dose
216. Unresolved toxicities from prior antitumor therapy, defined as not having resolved to Common Terminology Criteria for Adverse Events (CTCAE), version 4.0 grade 1 (with the exception of myelosuppression, eg, neutropenia, anemia, thrombocytopenia), or to levels dictated in the eligibility criteria with the exception of alopecia or toxicities from prior antitumor therapy that are considered irreversible (defined as having been present and stable for > 2 months) which may be allowed if they are not otherwise described in the exclusion criteria AND there is agreement to allow by both the investigator and sponsor
217. Antitumor therapy (chemotherapy, antibody therapy, molecular-targeted therapy such as FLT3 inhibitors, or investigational agent) within 14 days of day 1
 - Exception: hydroxyurea to control peripheral blood leukemic cell counts is allowed until start of investigational product treatment
 - Exception: antitumor therapies with short half-lives only require passing of 5 half-lives from last dose, and after discussion with sponsor
218. Treatment with systemic immune modulators including, but not limited to, non-topical systemic corticosteroids, cyclosporine, and tacrolimus within 2 weeks before enrollment (day 1)

- Exception: physiologic replacement steroids or steroids for treatment of transfusion/hypersensitivity reactions
219. Prior treatment with a FLT3 targeting CAR-T
220. Major surgery within 28 days of study day 1 with the exception of biopsy and insertion of central venous catheter
221. History or evidence of any other clinically significant disorder, condition or disease that, in the opinion of the investigator or Amgen medical monitor would pose a risk to subject safety or interfere with the study evaluation, procedures or completion
222. Males and females of reproductive potential who are unwilling to practice a highly effective method(s) of birth control while on study through 4 weeks after receiving the last dose of study drug. Acceptable methods of highly effective birth control include sexual abstinence (males, females); vasectomy; bilateral tubal ligation/occlusion; or a condom with spermicide (men) in combination with hormonal birth control or intrauterine device (IUD) (women)
223. Females who are lactating/breastfeeding or who plan to breastfeed while on study through 4 weeks after receiving the last dose of study drug
224. Females with a positive pregnancy test
225. Females planning to become pregnant while on study through 4 weeks after receiving the last dose of study drug
226. Subjects likely to not be available to complete all protocol-required study visits or procedures, and/or to comply with all required study procedures to the best of the subject's and investigator's knowledge
227. History of multiple sclerosis or any other demyelinating disease
228. Active hepatitis secondary to alcoholic hepatitis or nonalcoholic steatohepatitis
- 229. History or evidence of severe acute respiratory syndrome coronavirus 2 (SARS-CoV-2) infection unless agreed upon with Medical Monitor and meeting the following criteria:**
- **Negative test for SARS-CoV-2 RNA by reverse transcriptase-polymerase chain reaction (RT-PCR) within 72 hours of first dose of investigational product**
 - **No acute symptoms of coronavirus disease 2019 (COVID-19) disease within 10 days prior to first dose of investigational product (counted from day of positive test for asymptomatic subjects)**

5. SUBJECT ENROLLMENT

Before subjects begin participation in any study-specific activities/procedures, Amgen requires a copy of the site's written institutional review board/independent ethics committee (IRB/IEC) approval of the protocol, informed consent form (ICF), and all other subject information and/or recruitment material, if applicable (see Section 11.2). All subjects must personally sign and date the ICF before commencement of study-specific

activities/procedures. A subject is considered enrolled when they have met all the eligibility criteria. The Investigator is to document the enrollment decision and date in the subject's medical record.

Each subject who enters the screening period for the study (defined as the point at which the subject signs the informed consent) receives a unique subject identification number before any study procedures are performed. The subject identification number will be assigned manually. This number will be used to identify the subject throughout the clinical study and must be used on all study documentation related to that subject.

The unique subject identification number will consist of 11 digits. The first 3 digits will represent the last 3 digits of the protocol number (ie, 528). The next 5 digits will represent the country code and site number (eg, 66001) and will be identical for all subjects at the site. The next 3 digits will be assigned in sequential order as subjects are screened (eg, 001, 002, or 003). For example, the first subject to enter screening at site 66001 will receive the number [REDACTED], and the second subject at the same site will receive the number [REDACTED].

The subject identification number must remain constant throughout the entire clinical study; it must not be changed after initial assignment, including if a subject is rescreened.

Subjects who do not meet the eligibility criteria within the 14-day screening period will not be eligible for enrollment. Subjects may be re-screened up to 3 times at the discretion of the investigator. The subject must be re-consented if a re-screening attempt occurs outside the 14-day screening period. With the exception of hepatitis serology and bone marrow assessments, re-screened subjects who are re-consented will repeat all screening procedures. See Section 7.2.1 for assessments during re-screening. Subjects who are deemed ineligible will be documented as screen failures.

Subjects may be eligible to begin treatment once all screening tests and procedures are completed and results indicate that all eligibility criteria are met. A site representative will complete and send the enrollment eligibility worksheet to the sponsor or designee.

5.1 Treatment Assignment

An Amgen representative will notify the site(s) in writing when a cohort is open to screen new subjects. In the initial dose escalation cohorts, only a single subject will be enrolled to a cohort because the dose level is not anticipated to be clinically active. Evidence of

pharmacologic activity will trigger multiple subject enrollment in the same and all subsequent cohorts. Enrollment will be performed according to the BLRM design (see Section 3.1 for details) from the first multiple subject cohort onwards. Each multiple subject cohort will enroll up to 4 evaluable subjects.

At completion of the dose escalation cohorts, additional subjects, approximately 90 (FIH: N = 40, MRD+: N = 50) will be enrolled in a dose expansion cohorts to gain further clinical experience, safety and efficacy data in subjects with AMG 427. The dose to be evaluated will be at or below the MTD estimated in the dose escalation cohorts.

6. TREATMENT PROCEDURES

6.1 Classification of Product

Study treatment is defined as any investigational product(s), non-investigational product(s), placebo, or medical device(s) intended to be administered to a study subject according to the study protocol.

The Amgen investigational product used in this study is AMG 427.

In this study (starting with the etanercept (Enbrel) substudy [REDACTED]), etanercept (Enbrel® [investigational use of a marketed product]) will be used (US only) prophylactically to mitigate signs, symptoms, and severity of CRS. Etanercept is not FDA-approved for the disease/condition being studied. Etanercept will be manufactured and packaged by Amgen Inc. and distributed using Amgen clinical study drug distribution procedures.

6.2 Investigational Product

The investigational product will be administered at the research facility by a qualified staff member.

A physician or nurse trained in emergency procedures must be available when the infusion of investigational product is started for immediate intervention in case of complications.

6.2.1 Amgen Investigational Product AMG 427

AMG 427 will be manufactured and packaged by Amgen Inc., or its agents, and distributed using Amgen or its agents' clinical study drug distribution procedures.

AMG 427 is supplied as a sterile, preservative-free lyophilized powder for IV administration after reconstitution with sterile Water for Injection (WFI). After reconstitution with 1.2 mL of sterile WFI, the 1 mg/mL AMG 427 drug product is

formulated with ■ mM glutamic acid, ■% (w/v) sucrose, and ■% (w/v) polysorbate 80, pH ■. The final container is a single-use, 6R glass vial and contains a target extractable amount of 1 mg AMG 427.

The intravenous solution stabilizer (IVSS) is intended for pre-treatment of IV bags prior to dilution of AMG 427 drug product. The IVSS is supplied as a sterile solution in a 10-cc glass vial containing 10 mL deliverable product. The IVSS does not contain an active pharmaceutical ingredient and is a buffered, preservative-free solution (■ mM citric acid, ■ M lysine hydrochloride, ■% (w/v) polysorbate 80, pH ■).

6.2.1.1 Dosage, Administration, and Schedule

AMG 427 may be administered as short-term IV infusions, delivered using infusion pumps (for the higher doses) and syringe pumps (for the lower doses), respectively, which are both approved for use by the appropriate regulatory authority for the country in which the subject is undergoing treatment.

AMG 427 solution for infusion will be prepared in bags for IV infusion and delivered through infusion lines. An IV flush bag will be connected to the IV infusion line after AMG 427 dose infusion is completed to administer a controlled rate post-infusion flush. The drug will be administered as short-term IV infusions (approximately 90 minutes) on D1, D3 (if applicable), D5, and D8 (if applicable) of each treatment cycle followed by an infusion-free interval prior to the start of the following treatment cycle. AMG 427 solution will be prepared in bags for short or eIV infusion and delivered through infusion lines.

The first eIV group will start at a DLRT-approved dose level from the FIH group, eg, if DLRT approves as safe and tolerable, the following dosing regimen will be administered:

- Days 1 and 2: eIV of ■ μg (over approximately 48 hours, with approximately 12-hour bag changes)
- Day 3: eIV of ■ μg (over approximately 24 hours, with approximately 12-hour bag changes)
- Day 5: short IV of ■ μg (over approximately 90 minutes)
- Day 8: short IV of ■ μg (over approximately 90 minutes)

Subsequent eIV cohorts will use the same dose levels as the FIH (short IV) cohorts (Table 4).

[figure not shown]
Two additional infusions, on D12 and D19 of each cycle, may be implemented by DLRM recommendation. The infusion-free interval will have a duration of 1 to 5 weeks (depending on treatment response), but may be extended to up to 7 weeks in case of

prolonged marrow aplasia and aleukemic cytopenias after consultation with the sponsor. It may also be extended for up to 3 days from the planned duration if necessary for logistical reasons. For further details on planned dosing and infusion details can be provided if needed, please also see Section 3.1.

The planned dose levels for the dose escalation cohorts are: [REDACTED] μg . The MTD or highest tested dose (or doses, in case of dose step) will be administered in the dose-expansion cohort.

After completion of a first cycle without DLT, up to 11 additional treatment cycles can be administered as long as in the judgment of the investigator the subject is deriving benefit.

The duration of the infusion-free interval between the last infusion of a treatment cycle and the D1 infusion of the subsequent cycle is dependent on treatment response and recovery of blood counts (see below and Figure 4 for details). It may also be extended for up to 3 days from the planned duration, if necessary, for logistical reasons. The DLRT may recommend on changes of the duration of the infusion-free interval for future cohorts after evaluation of PK data.

The infusion-free interval may be extended up to a maximum of 7 weeks in case of insufficient recovery of peripheral blood counts in the absence of active AML (neutrophils $> 500/\mu\text{L}$, platelets $> 20\,000/\mu\text{L}$)

AML = acute myeloid leukemia; BM = bone marrow; D = day

* Myeloblasts must be confirmed by flow-cytometry based immunophenotype

The infusion-free interval may be extended up to a maximum of 7 weeks in case of insufficient recovery of peripheral blood counts back to baseline or neutrophils $> 500/\mu\text{L}$,

platelets > 20 000/ μ L without transfusion in the absence of active AML, after consultation with the sponsor. In case the infusion--free interval is extended to 7 weeks, a bone marrow assessment is recommended 5 weeks after the last infusion of a cycle. In case this assessment shows leukemic infiltration of the bone marrow (\geq 5% blasts), treatment should be resumed immediately even if peripheral blood counts have not yet recovered at this time point.

Hospitalization

Subjects will be hospitalized for a minimum of 8 or 11 days from the start of the first dose in cycle 1 (ie, until at least 72 hours after D5 or D8, depending on schedule) and for a minimum of 72 hours following D12 and D19 doses in cycle 1. If the subject receives a second subsequent cycle of AMG 427 at the same dose, hospitalization will be for a minimum of 8 or 11 days from start of the day 1 dose (ie, at least 72 hours after D5 or D8, depending on schedule). Hospitalization following D12 and D19 doses in cycle 2 and onwards will be at the discretion of the treating physician. For subjects receiving > 2 cycles, hospitalization for cycle 3 onwards for all doses will be at the treating physician's discretion.

Additionally, subjects will be hospitalized for a minimum of 72 hours under the following circumstances:

- after each new dose step, if applicable
- after dose increase in case of intra-subject dose escalation
- after re-start of treatment after an interruption due to adverse event

Subjects can be hospitalized for a longer time period at the discretion of the investigator.

Hospitalization requirements may be reduced for subjects enrolled in the dose expansion phase based on cumulative safety and tolerability data from the dose escalation phase, by DLRT recommendation.

A nurse trained in emergency procedures or a physician must be available when the dose of AMG 427 is started for immediate intervention in case of complications. The hospitalization period may be extended at the discretion of the investigator. During hospitalization periods, an immediately accessible emergency room with resuscitation equipment must be available.

Prior to hospital discharge, vital signs will be measured in order to detect possible signs and symptoms of CRS. If required for logistical reasons (eg, long travel times), subjects may be hospitalized the day before start of dosing (eg, day -1).

The start time of dose should be chosen carefully so as to avoid any interference or inconvenience with time points of safety assessments or PK/PD measurements. The site should record any unscheduled interruption of a dose on the electronic case report form (eCRF), and provide the start and stop date/time of the infusion.

AMG 427 should be administered through a central venous access at a constant flow rate. The drug should not be administered as a bolus. In the event that administration through a central venous access is not possible, AMG 427 may be administered through a peripheral venous line.

The concentration, quantity administered, start date/time, stop date/time, and lot number of investigational product are to be recorded on each subject's eCRF.

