Subjects will be hospitalized for a minimum of 8 or 11 days from the first dose in cycle 1 (ie, at least 72 hours after the day 5 or day 8 dose, depending on the schedule) and for a minimum of 72 hours following day 12 and day 19 doses in cycle 1 (if applicable). If the subject receives a second cycle of AMG 427 at the same dose, hospitalization will be for a minimum of 8 or 11 days from the start of the day 1 dose (ie, at least 72 hours after the day 5 or day 8 dose, depending on the schedule) in cycle 2. Hospitalization following day 12 and day 19 doses (if applicable) in cycle 2 and onwards will be at the discretion of the treating physician. For subjects receiving > 2 cycles, hospitalization for cycle 3 onwards for all doses will be at the treating physician's discretion. However, in case of intra-subject dose escalation (ISDE), subjects will be hospitalized as per the guidance for the first cycle. After re-start of treatment, following an interruption due to an adverse event(s), the subject will be hospitalized for a minimum of 72 hours. Subjects can be hospitalized for a longer time period at the discretion of the investigator. A nurse trained in emergency procedures or a physician must be available when the dose of AMG 427 is started for immediate intervention in case of complications.

The planned dose levels for the dose escalation cohorts are: [REDACTED] µg. Lower intermediate doses may be implemented based on BLRM and DLRT recommendations. The MTD or a lower dose will be administered in the dose expansion cohort.

A total of up to 12 total treatment cycles can be administered as long as in the judgment of the investigator the subject is deriving benefit and does not meet the criteria for permanent discontinuation of the drug (Section 6.2.1.4).

Procedures:

After providing informed consent, eligible subjects will undergo the following assessments during this study: physical examination, Eastern Cooperative Oncology Group (ECOG) status, height, weight, vital signs, pulse oximetry, electrocardiogram (ECG) triplicate measurements, laboratory assessments (including serum pregnancy test, if applicable, coagulation, hematology, chemistry, urinalysis, hepatitis serology, and [REDACTED]), biomarker and PK assessments, and bone marrow assessments. For a full list of study procedures, including the timing of each procedure, please refer to Section 7 of the study protocol and the Schedule of Assessments (Table 10 to Table 23).

Statistical Considerations:

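### After intra-subject dose escalation the synopsis requires the full cycle 1 hospital stay, but Section 6.2.1.1, where sites are sent, requires only 72 hours

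*Protocol*

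**What the plan says.** **Protocol Synopsis, dosage and administration.** Cycle 1 requires at least 8 or 11 days in hospital, that is, until 72 hours after the D5 or D8 dose, plus 72 hours after each of D12 and D19 if given. Cycle 2 at the same dose keeps the 8 or 11 days. D12 and D19 stays from cycle 2, and all stays from cycle 3, are left to the physician. The synopsis then makes an exception: "However, in case of intra-subject dose escalation (ISDE), subjects will be hospitalized as per the guidance for the first cycle". It uses 72 hours for a different case, a restart: "following an interruption due to an adverse event(s), the subject will be hospitalized for a minimum of 72 hours".

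**Protocol Section 6.2.1.1, Hospitalization.** The base rules are the same. The 8 or 11 day stay in cycle 2 applies if the subject "receives a second subsequent cycle of AMG 427 at the same dose". The discretion sentences are also there: "Hospitalization following D12 and D19 doses in cycle 2 and onwards will be at the discretion of the treating physician", and "For subjects receiving > 2 cycles, hospitalization for cycle 3 onwards for all doses" is likewise the physician's decision. The synopsis exception is absent. A list of cases with a 72-hour minimum follows: each new dose step, a restart after an adverse event, and "after dose increase in case of intra-subject dose escalation". The section adds that "Subjects can be hospitalized for a longer time period at the discretion of the investigator".

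**Where sites are sent.** Section 7.2.2 and the schedule footnotes (for example, footnote c of Table 20) refer to Section 6.2.1.1 for hospitalization requirements. Nothing reconciles the two rules.

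**The concern.** The hospital stay is a safety minimum for CRS. Section 2.2.4 reports CRS in 42 of 53 subjects (79.2%), serious in 8 (15.1%) and fatal in 1. Amendment 7 was written after a partial clinical hold for the fatal event, and Section 6.6 names the period after a dose step as one of increased risk.

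A site that follows only Section 6.2.1.1 could discharge an escalated subject before the D5 or D8 dose of that cycle, which the synopsis does not allow. Leaving hospital can also reduce monitoring. Under Section 7.2.2, only ECG and PK sampling return to an early-cycle schedule after intra-subject escalation; other assessments follow the actual cycle. In Table 18 (cycle 3 onwards) and Table 20 (cycle 2, six doses), vital signs and pulse oximetry after the end of dosing are needed only while the subject is still at the clinic.

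**Working it through.** **The plan's own figures.** 72 hours is 3 days. D5 + 3 = D8 and D8 + 3 = D11, which reproduces the stated 8 or 11 days.

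**Does Section 6.2.1.1 give an escalated cycle any base stay?** It does not. Its 8 or 11 days cover cycle 1 and a second cycle at an unchanged dose, and from cycle 3 everything is discretionary. The 72 hours is introduced as an addition, but for this cycle there is nothing to add it to.

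**End of the minimum stay, D1/D3/D5/D8, short infusions.** The synopsis minimum runs from D1 to D11, or 11 − 1 = 10 elapsed days. The Section 6.2.1.1 minimum ends 3 days after the last dose that counts as an increase.

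| Last counted increase | Section 6.2.1.1 minimum ends | Earlier than D11 |
|---|---|---|
| D1 | 1 + 3 = D4 | 7 days |
| D3 | 3 + 3 = D6 | 5 days |
| D5 | 5 + 3 = D8 | 3 days |
| D8 | 8 + 3 = D11 | 0 days |

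**Inpatient days required.** Each counted increase at day d covers d to d + 3, and overlaps are merged. If all four doses count, D1 to D11 is covered without a gap, giving 10 of 10 days. If one counts, 3 of 10 are covered. The shortfall is therefore 0 to 7 days, and it is 0 only if all four count.

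The result depends on whether an increase means a new highest dose for the subject or any dose above the same day's dose in the prior cycle. Dose levels are redacted, so the two patterns below are assumptions.

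| Assumed pattern | New highest dose | Raised against prior cycle |
|---|---|---|
| One higher flat dose on all four days | D1 counts; ends D4; 3 of 10 days | All four count; ends D11; 10 of 10 days |
| D1 and D3 run-in unchanged; one higher target dose on D5 and D8 | D5 counts; ends D8; 3 of 10 days | D5 and D8 count; ends D11; 6 of 10 days (D5 to D11) |

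**Extended infusion (eIV).** The D1 dose runs "over approximately 48 hours, with approximately 12-hour bag changes" and the D3 dose runs about 24 hours. Counting 72 hours from the end of infusion, an increase at D1 only gives 1 + 2 + 3 = D6 (5 days earlier than D11). A last increase at D3 gives 3 + 1 + 3 = D7 (4 days earlier).

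**Six-dose cycles.** The synopsis adds stays to 12 + 3 = D15 and 19 + 3 = D22. Section 6.2.1.1 leaves both to the physician unless that dose is itself an increase.

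**The case against.** The strongest reply is that the two rules do not force a breach. Both are minimums in one protocol, the longer stay satisfies both, and investigators may extend. That is true, and it limits the seriousness. It does not make the texts agree, because a site working only from Section 6.2.1.1 can fall short of the synopsis.

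A second reply is that Section 6.2.1.1 already covers the riskiest doses: each new highest dose brings its own 72 hours, and escalation is open only to subjects without a DLT, moving to a level the Dose Level Review Team (DLRT) has deemed safe. This also stands in part. Section 6.6 speaks of the first few days without giving a length, so nothing here shows that 72 hours after one increase is too short. The exposed doses are later ones in the cycle that are not new highs.

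Third, the 7-day figure needs an increase that counts only at D1, whereas Sections 2.4.3 and 3.1.2.2 describe a run-in dose held at MTD1 with later doses raised. That is fair; under that pattern the stay ends 0 to 3 days early, although no stay is then required before the first raised dose.

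Finally, 72 hours may be the intended rule and the synopsis the text in error. The documents do not settle this. While both stand, the longer one governs a compliant site. The hospitalization row of the schedule tables is blank in the public text and could not be checked.

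**Conclusion.** The concern holds. This is an internal inconsistency in a safety rule, and the section that sites are sent to states the shorter minimum. On D1/D3/D5/D8 with short infusions, the Section 6.2.1.1 minimum ends 0 to 7 days before the synopsis minimum. The size is conditional on the redacted dose levels and on the undefined meaning of a dose increase. The number of subjects who escalate is not given, so the total effect cannot be stated. No endpoint, estimate, DLT definition or stopping boundary is affected. It should be corrected, because the error sits in an operative safety instruction and is simple to remove.

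**What to change.** In Section 6.2.1.1, replace the 72-hour bullet for intra-subject escalation with the synopsis rule: such a cycle follows the cycle 1 minimum of 8 or 11 days from D1, plus 72 hours after each of D12 and D19 if given. Add a clause exempting these cycles from the two physician-discretion sentences (D12 and D19 doses from cycle 2, and all doses from cycle 3). Leave unchanged the option for the DLRT to reduce stays in the expansion phase. If the sponsor does intend 72 hours, the synopsis must change instead, with a reason and a definition of which doses count as an increase.

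The cost is one bullet and one clause in an amendment. Compared with Section 6.2.1.1 as written, it adds 0 to 7 inpatient days per escalated D1/D3/D5/D8 cycle, and up to two 72-hour stays if D12 and D19 are given. Compared with the synopsis it adds nothing.
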